### **12.2 Data Reporting**

#### **12.2.1 Method**

Data collection for this study will be done exclusively through Medidata Rave. Access to the trial in Rave is granted through the iMedidata application to all persons with the appropriate roles assigned in the Regulatory Support System (RSS). To access Rave via iMedidata, the site user must have an active CTEP IAM account (check at <https://ctepcore.nci.nih.gov/iam>) and the appropriate Rave role (Rave CRA, Read-Only, CRA, Lab Admin, SLA or Site Investigator) on either the LPO or participating organization roster at the enrolling site. To hold Rave CRA role or CRA Lab Admin role, the user must hold a minimum of an AP registration type. To hold the Rave Site Investigator role, the individual must be registered as an NPIVR or IVR. Associates can hold read-only roles in Rave.

Upon initial site registration approval for the study in RSS, all persons with Rave roles assigned on the appropriate roster will be sent a study invitation e-mail from iMedidata. To accept the invitation, site users must log into the Select Login (<https://login.imedidata.com/selectlogin>) using their CTEP-IAM user name and password, and click on the “accept” link in the upper right-corner of the iMedidata page. Please note, site users will not be able to access the study in Rave until all required Medidata and study specific trainings are completed. Trainings will be in the form of electronic learnings (eLearnings), and can be accessed by clicking on the link in the upper right pane of the iMedidata screen.

Users that have not previously activated their iMedidata/Rave account at the time of initial site registration approval for the study in RSS will also receive a separate invitation from iMedidata to activate their account. Account activation instructions are located on the CTSU website, Rave tab under the Rave resource materials (Medidata Account Activation and Study Invitation Acceptance). Additional information on iMedidata/Rave is available on the CTSU members’ website under the Rave tab or by contacting the CTSU Help Desk at [name] or by e-mail at [[contact]](mailto:[contact]).

This study will be monitored by the Clinical Trials Monitoring Service (CTMS). Data will be submitted to CTMS at least once every two weeks via Medidata Rave (or other modality if approved by CTEP). Information on CTMS reporting is available at <http://www.theradex.com/clinicalTechnologies/?National-Cancer-Institute-NCI-11>. On-site audits will be conducted three times annually (one annual site visit and two data audits). For CTMS monitored studies, after users have activated their accounts, please contact the Theradex Help Desk at [contact] or by email at [[contact]](mailto:[contact]) for additional support with Rave and completion of CRFs.

### 12.2.2 Responsibility for Data Submission

For ETCTN trials, it is the responsibility of the PI(s) at the site to ensure that all investigators at the ETCTN Sites understand the procedures for data submission for each ETCTN protocol and that protocol specified data are submitted accurately and in a timely manner to the CTMS via the electronic data capture system, Medidata Rave.

Data are to be submitted via Medidata Rave to CTMS on a real-time basis, but no less than once every 2 weeks. The timeliness of data submissions and timeliness in resolving data queries will be tracked by CTMS. Metrics for timeliness will be followed and assessed on a quarterly basis. For the purpose of Institutional Performance Monitoring, data will be considered delinquent if it is greater than 4 weeks past due.

Data from Medidata Rave and CTEP-AERS is reviewed by the CTMS on an ongoing basis as data is received. Queries will be issued by CTMS directly within Rave. The queries will appear on the Task Summary Tab within Rave for the CRA at the ETCTN to resolve. Monthly web-based reports are posted for review by the Drug Monitors in the IDB, CTEP. Onsite audits will be conducted by the CTMS to ensure compliance with regulatory requirements, GCP, and NCI policies and procedures with the overarching goal of ensuring the integrity of data generated

from NCI-sponsored clinical trials, as described in the ETCTN Program Guidelines, which may be found on the CTEP ([http://ctep.cancer.gov/protocolDevelopment/electronic\\_applications/adverse\\_events.htm](http://ctep.cancer.gov/protocolDevelopment/electronic_applications/adverse_events.htm)) and CTSU websites.

An End of Study CRF is to be completed by the PI, and is to include a summary of study endpoints not otherwise captured in the database, such as (for phase 1 trials) the recommended phase 2 dose (RP2D), and a description of any dose-limiting toxicities (DLTs). CTMS will utilize a core set of eCRFs that are Cancer Data Standards Registry and Repository (caDSR) compliant (<http://cbiit.nci.nih.gov/ncip/biomedical-informatics-resources/interoperability-and-semantics/metadata-and-models>). Customized eCRFs will be included when appropriate to meet unique study requirements. The PI is encouraged to review the eCRFs, working closely with CTMS to ensure prospectively that all required items are appropriately captured in the eCRFs prior to study activation. CTMS will prepare the eCRFs with built-in edit checks to the extent possible to promote data integrity.

CDUS data submissions for ETCTN trials activated after March 1, 2014, will be carried out by the CTMS contractor, Theradex. CDUS submissions are performed by Theradex on a monthly basis. The trial's lead institution is responsible for timely submission to CTMS via Rave, as above.

Further information on data submission procedures can be found in the ETCTN Program Guidelines ([http://ctep.cancer.gov/protocolDevelopment/electronic\\_applications/adverse\\_events.htm](http://ctep.cancer.gov/protocolDevelopment/electronic_applications/adverse_events.htm)).

### **12.3 Collaborative Agreements Language**

The agent(s) supplied by CTEP, DCTD, NCI used in this protocol is/are provided to the NCI under a Collaborative Agreement (CRADA, CTA, CSA) between the Pharmaceutical Company(ies) (hereinafter referred to as "Collaborator(s)") and the NCI Division of Cancer Treatment and Diagnosis. Therefore, the following obligations/guidelines, in addition to the provisions in the "Intellectual Property Option to Collaborator" ([http://ctep.cancer.gov/industryCollaborations2/intellectual\\_property.htm](http://ctep.cancer.gov/industryCollaborations2/intellectual_property.htm)) contained within the terms of award, apply to the use of the Agent(s) in this study:

1. Agent(s) may not be used for any purpose outside the scope of this protocol, nor can Agent(s) be transferred or licensed to any party not participating in the clinical study. Collaborator(s) data for Agent(s) are confidential and proprietary to Collaborator(s) and shall be maintained as such by the investigators. The protocol documents for studies utilizing Agents contain confidential information and should not be shared or distributed without the permission of the NCI. If a copy of this protocol is requested by a patient or patient's family member participating on the study, the individual should sign a confidentiality agreement. A suitable model agreement can be downloaded from: <http://ctep.cancer.gov>.

2. For a clinical protocol where there is an investigational Agent used in combination with (an)other Agent(s), each the subject of different Collaborative Agreements, the access to and use of data by each Collaborator shall be as follows (data pertaining to such combination use shall hereinafter be referred to as "Multi-Party Data"):
  - a. NCI will provide all Collaborators with prior written notice regarding the existence and nature of any agreements governing their collaboration with NCI, the design of the proposed combination protocol, and the existence of any obligations that would tend to restrict NCI's participation in the proposed combination protocol.
  - b. Each Collaborator shall agree to permit use of the Multi-Party Data from the clinical trial by any other Collaborator solely to the extent necessary to allow said other Collaborator to develop, obtain regulatory approval or commercialize its own Agent.
  - c. Any Collaborator having the right to use the Multi-Party Data from these trials must agree in writing prior to the commencement of the trials that it will use the Multi-Party Data solely for development, regulatory approval, and commercialization of its own Agent.
3. Clinical Trial Data and Results and Raw Data developed under a Collaborative Agreement will be made available to Collaborator(s), the NCI, and the FDA, as appropriate and unless additional disclosure is required by law or court order as described in the IP Option to Collaborator ([http://ctep.cancer.gov/industryCollaborations2/intellectual\\_property.htm](http://ctep.cancer.gov/industryCollaborations2/intellectual_property.htm)). Additionally, all Clinical Data and Results and Raw Data will be collected, used and disclosed consistent with all applicable federal statutes and regulations for the protection of human subjects, including, if applicable, the *Standards for Privacy of Individually Identifiable Health Information* set forth in 45 C.F.R. Part 164.
4. When a Collaborator wishes to initiate a data request, the request should first be sent to the NCI, who will then notify the appropriate investigators (Group Chair for Cooperative Group studies, or PI for other studies) of Collaborator's wish to contact them.
5. Any data provided to Collaborator(s) for Phase 3 studies must be in accordance with the guidelines and policies of the responsible Data Monitoring Committee (DMC), if there is a DMC for this clinical trial.
6. Any manuscripts reporting the results of this clinical trial must be provided to CTEP by the Group office for Cooperative Group studies or by the principal investigator for non- Cooperative Group studies for immediate delivery to Collaborator(s) for advisory review and comment prior to submission for publication. Collaborator(s)

will have 30 days from the date of receipt for review. Collaborator shall have the right to request that publication be delayed for up to an additional 30 days in order to ensure that Collaborator's confidential and proprietary data, in addition to Collaborator(s)'s intellectual property rights, are protected. Copies of abstracts must be provided to CTEP for forwarding to Collaborator(s) for courtesy review as soon as possible and preferably at least three (3) days prior to submission, but in any case, prior to presentation at the meeting or publication in the proceedings. Press releases and other media presentations must also be forwarded to CTEP prior to release. Copies of any manuscript, abstract and/or press release/ media presentation should be sent to:

Email: [contact]

The Regulatory Affairs Branch will then distribute them to Collaborator(s). No publication, manuscript or other form of public disclosure shall contain any of Collaborator's confidential/ proprietary information.

## 13. STATISTICAL CONSIDERATIONS

### 13.1 Study Design/Endpoints

#### 13.1.1 Primary Objectives

To determine the recommended phase II dose (RP2D) and safety profile of AZD1775 in combination with radiotherapy and concurrent cisplatin patients with gynecological cancer (phase I).

The proportion of patients who experience DLT will be recorded for all patients in dose escalation and dose expansion. Because toxicities can be cumulative, the proportion of patients evaluable for toxicity requiring treatment discontinuation or dose reduction/interruption at any time through the duration of therapy will also be recorded.

The first dose level will be level 1. If 1/3 patients encounter a dose-limiting toxicity (DLT), then a cohort will be expanded to 6 patients. If > 2/3 of patients encounter DLT, then that dose level will be declared excessively toxic. A total of 6 patients will be entered into the previous dose level. The recommended phase II dose (RPTD; also called the MTD) is defined as the dose level with < 1/6 patients with DLT.

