#### Dose Escalation

A cohort of 3 patients per dose level are planned:

- The starting dose will be dose level (DL) 1, AZD1775 will be administered on Day 1, 3, and 5 of each week
- If AZD1775 is tolerable at DL1 with no DLT experienced, 3 patients enter DL2.
- If AZD1775 is tolerable at DL2 with no DLT experienced, 3 patients enter DL3.
- If AZD1775 is tolerable at DL3 with no DLT experienced, 3 patients enter DL4 of which AZD1775 will be administered Day 1-5 of the week.

If the first 2 patients enrolled in a starting dose level (DL1) experience DLT, further enrollment

to that dose level will stop and a lower dose level will be explored. If the first 2 patients enrolled in the lower dose level (DL-1) experience DLT, further enrollment to that dose level will stop. The Principal Investigator will discuss with the sponsors regarding the appropriate next step.

If 1/3 patients encounter a dose-limiting toxicity (DLT), then the cohort will be expanded to 6 patients. If  $\geq 2/6$  of patients encounter DLT, then that dose level will be declared excessively toxic. A total of 6 patients will be entered into the previous dose level.

The recommended phase II dose (RPTD; also called the MTD) is defined as the dose level with  $\leq 1/6$  patients with DLT.

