### 5.2.2 Non-hematologic DLT

- Grade 4 vomiting, or grade 3 vomiting if persistent for longer than 48 hours despite treatment with granisetron, ondansetron or an equivalent medication.
- Grade 4 diarrhea, or grade 3 diarrhea if persistent for longer than 48 hours despite treatment with loperamide, diphenoxylate/atropine or an equivalent medication.
- Grade 3 or 4 rash
- Other grade 3 or 4 radiotherapy associated acute toxicity
- Interruption of whole pelvis radiotherapy for more than 3 days due to acute treatment toxicity
- Inability to receive at least 3 of the 5 planned doses of cisplatin
- If the patient requires an omission longer than 1 week in the administration of AZD1775 and/or cisplatin
- Any grade 3 or 4 non-hematological toxicity with the specific exception of:
  - Nausea, vomiting, diarrhea, or dehydration (all Grade 3) not optimally treated and/or lasts less than 48 hours.
  - Alopecia (of any grade)
  - Inadequately treated hypersensitivity reactions
  - Clinically non-significant, treatable or reversible lab abnormalities including, but not limited to liver function tests, uric acid, hypokalemia or hypomagnesemia.

[Note: reversible G3 and G4 electrolyte disturbances will be considered those that improve, at least to G2, within 48h when optimally treated]

---

 An adverse event or any delay not related to the study medication will not be considered DLT

Management and dose modifications associated with the above adverse events are outlined in [Section 6](#). Dose escalation will proceed within each cohort according to [Table 5-3](#). Dose-limiting toxicity (DLT) is defined above in [Section 5.2](#).

Table 5-3: Dose escalation schema

Number of Patients with DLT at a Given Dose Level	Escalation Decision Rule
0 out of 3	Enter 3 patients at the next dose level.
$\geq 2$	Dose escalation will be stopped. This dose level will be declared the maximally administered dose (highest dose administered). Three (3) additional patients will be entered at the next lowest dose level if only 3 patients were treated previously at that dose.

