1 out of 3	
Enter at least 3 more patients at this dose level.
 
 
• If 0 of these 3 patients experience DLT, proceed to the next dose level.
 
• If 1 or more of this group suffer DLT, then dose escalation is stopped, and this dose is declared the maximally administered dose. Three (3) additional patients will be entered at the next lowest dose level if only 3 patients were treated previously at that dose.
 

$\leq 1$ out of 6 at highest dose level below the maximally administered dose	
This is generally the recommended phase 2 dose.
 
Once the provisional recommended phase 2 dose is found, 9-12* patients will be enrolled in the expansion cohort to confirm the safety of this dose.
 
*The final number of patients evaluated at the recommended phase 2 dose will be 15:
 
 
• If 3 patients have been previously enrolled during the dose escalation phase, 12 additional patients will be evaluated in the dose expansion phase
 
• If 6 patients have been previously enrolled during the dose escalation phase, 9 additional patients will be enrolled in the dose escalation
 

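### Section 13.1.1 puts the toxicity cut-off at 2/3 where the rest of the protocol uses two or more DLTs, so 2/6 and 3/6 have no toxic call or next step there

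*Combined protocol and SAP*

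**What the plan says.** Section 13.1.1 gives a short dose-decision rule. It expands after one DLT in three: "If 1/3 patients encounter a dose-limiting toxicity (DLT), then a cohort will be expanded to 6 patients". It then sets the toxic threshold, "If > 2/3 of patients encounter DLT, then that dose level will be declared excessively toxic", sends the trial back to the previous level to make up 6 patients there, and says that the recommended phase II dose "is defined as the dose level with < 1/6 patients with DLT".

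The Dose Escalation text in the Study Summary, repeated in Section 5.1.1, follows the same sequence with other thresholds: "If $\geq 2/6$ of patients encounter DLT, then that dose level will be declared excessively toxic", and the recommended dose "is defined as the dose level with $\leq 1/6$ patients with DLT". The Dose Expansion text in both places uses the same two cut-offs.

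Table 5-3 is the operative schema; Section 5.2.2 introduces it with "Dose escalation will proceed within each cohort according to". It stops escalation at two or more DLTs. After 1/3 it says "If 1 or more of this group suffer DLT, then dose escalation is stopped, and this dose is declared the maximally administered dose", which means a total of at least 2/6. The next step is also given: "Three (3) additional patients will be entered at the next lowest dose level if only 3 patients were treated previously at that dose".

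I found no statement of which section prevails if Sections 5 and 13 differ.

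**The concern.** The RP2D is the primary output, and Section 13 is where its rule is stated for analysis. That section creates a cohort of 6 after 1/3, but its toxic threshold does not reach the commonest unfavourable results of that cohort, 2/6 and 3/6. Elsewhere those results stop escalation and send patients to the lower level; in Section 13.1.1 they lead nowhere. If the printed strict sign in the RP2D definition is meant literally, Section 13.1.1 also refuses the RP2D label at 1/6, which the other passages accept. A report written to Section 13 could then disagree with the escalation decisions actually taken.

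**Working it through.** **Plan's own figure.** Section 13.2 gives a maximum of 24 patients in dose finding and 33 in all: 4 levels × 6 = 24, and 24 + 9 = 33. This reproduces, but the concern does not depend on it.

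**Outcomes side by side.** A level expanded after 1/3 can end only at 1/6 to 4/6. Section 13.1.1 is read three ways: signs as printed (> 2/3, < 1/6); signs as ≥ and ≤ with 2/3 as a fraction; and signs as ≥ and ≤ with 2/3 meaning 2 of the first 3 patients.

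| Outcome | Study Summary, 5.1.1, Table 5-3 | 13.1.1 as printed | 13.1.1, ≥ 2/3 as fraction | 13.1.1, ≥ 2 of first 3 |
|---|---|---|---|---|
| 2/3 | stop | no call | toxic | toxic |
| 3/3 | stop | toxic | toxic | toxic |
| 1/6 | acceptable | not toxic, not RP2D | acceptable | acceptable |
| 2/6 | stop | not toxic, not RP2D | not toxic, not RP2D | not toxic, not RP2D |
| 3/6 | stop | not toxic, not RP2D | not toxic, not RP2D | not toxic, not RP2D |
| 4/6 | stop | not toxic, not RP2D | toxic | not toxic, not RP2D |

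The 2/6 and 3/6 rows conflict on all three readings.

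**How often.** The documents give no DLT rate, so I assume p = 0.10, 0.20, 1/3, 0.40 and 0.50. DLTs are taken as independent, for one level with 3 patients, expanded to 6 only after 1/3. With q = 1 − p:

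- A. Toxic or stop under Section 5.1.1 and Table 5-3: 1 − q³ − 3pq²·q³
- B. Toxic under 13.1.1, ≥ 2/3 as a fraction: 3p²q + p³ + 3pq²·p³
- C. Toxic under 13.1.1, ≥ 2 of the first 3: 3p²q + p³
- D. Toxic under 13.1.1 as printed (only 3/3): p³
- E. Ends at 2/6 or 3/6: 3pq²·(3pq² + 3p²q)
- F. Ends at 1/6: 3pq²·q³

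At p = 0.20: q³ = 0.512, 3pq² = 0.384, 3p²q = 0.096, p³ = 0.008. Then

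- A = 1 − 0.512 − 0.384 × 0.512 = 0.291
- B = 0.096 + 0.008 + 0.384 × 0.008 = 0.107
- C = 0.104
- D = 0.008
- E = 0.384 × 0.480 = 0.184
- F = 0.384 × 0.512 = 0.197

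| p | A | B | C | D | E | F |
|---|---|---|---|---|---|---|
| 0.10 | 0.094 | 0.028 | 0.028 | 0.001 | 0.066 | 0.177 |
| 0.20 | 0.291 | 0.107 | 0.104 | 0.008 | 0.184 | 0.197 |
| 1/3 | 0.572 | 0.276 | 0.259 | 0.037 | 0.296 | 0.132 |
| 0.40 | 0.691 | 0.380 | 0.352 | 0.064 | 0.311 | 0.093 |
| 0.50 | 0.828 | 0.547 | 0.500 | 0.125 | 0.281 | 0.047 |

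Check: A − B equals E at every rate, so on the fraction reading the whole difference from Table 5-3 is 2/6 and 3/6. On the count reading 4/6 is uncovered as well, and the gap is A − C = 0.066, 0.187, 0.313, 0.339, 0.328.

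**The case against.** The strongest reply is that this is an omission and not a rival threshold. The preceding sentence of Section 13.1.1 uses 1/3 to mean one of three patients, so 2/3 most naturally means two of three. Read that way it matches the row for two or more DLTs in Table 5-3, and only a line for the cohort of 6 is missing. The bare signs are probably conversion losses. A literal < 1/6 could never be met by a level expanded after 1/3, which would make the expansion pointless. With ≥ and ≤, Section 13.1.1 accepts and refuses the same six-patient results as Section 5.1.1. Table 5-3 governs escalation, and Section 12.1 requires the Principal Investigator to sign off each dose decision.

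Most of this stands. The literal-sign results (columns D and F) deserve little weight until the source is checked. The RP2D is not misassigned under ≥ and ≤. The probabilities compare written rules and do not forecast conduct. It is also fair that the Dose Escalation text has no explicit line for 2/3 at levels 2 to 4 and relies on Table 5-3 for it.

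None of it closes the gap. The count reading leaves Section 13.1.1 with no toxic rule for the cohort that it creates itself, and adds 4/6 to the uncovered outcomes. Table 5-3 supplies the missing decision only because a reader goes outside Section 13, which does not refer to it.

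**Conclusion.** The concern holds. Section 13.1.1 contradicts the Study Summary, Section 5.1.1 and Table 5-3 on the toxic threshold, and at 2/6 and 3/6 this does not depend on how its signs or its 2/3 are read. Those two outcomes together have probability 7% to 31% per level across assumed DLT rates of 10% to 50%, given independent DLTs and expansion only after 1/3. What is lost is the toxic call and the de-escalation step in the statistical section. Only if the strict sign is literal does the RP2D label itself differ, at 1/6, an outcome with probability 5% to 20% over the same rates. Because Table 5-3 directs escalation, this should be corrected but does not show that conduct would go wrong. I take no view on which threshold is clinically right.

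**What to change.** Reconcile the passages so that one decision table governs. The simplest way is to delete the duplicate rule from Section 13.1.1 and cross-refer to a single table that assigns a decision and a next step to every outcome of 3 and of 6 patients. These include 2/3, 2/6, 3/6 and 4/6, and the results of a lower level filled from 3 to 6. Use identical fractions and inequality signs in the Study Summary, Section 5.1.1, Table 5-3 and Section 13. The sponsor should confirm which thresholds are intended and check the signs in Section 13.1.1 against the source document. The cost is a wording amendment to one paragraph and a consistency check of the others, with no added patients or analyses.
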